6.5.3.5. Dose escalations

Applicable to axitinib only. Dose escalation is defined as a change to a dose level higher than that planned in the protocol.

Number and percentage of patients with at least one dose escalation as well as a breakdown of dose escalations (1, 2, ≥3) will be summarized.

6.5.3.6. Dose interruptions

Applicable to axitinib and sunitinib.

An interruption is defined a 0 mg dose administered on one or more days for axitinib or within the dosing period of a cycle for sunitinib. What follows defines how dose interruptions will be counted in the case of multiple dose interruptions.

- If an interruption occurs consecutively for at least two days due to the same reason, then it will be counted only once (example: If the actual dose on days 1-3 is 10 mg and actual dose on days 4-5 is 0 mg and dose interruption on days 4-5 is due to AE, then the total number of dose interruptions is 1).
- If an interruption occurs consecutively for at least two days due to different reasons, then it will be counted for each reason (example: If the actual dose on days 1-3 is 10 mg and actual dose on days 4-5 is 0 mg and dose interruption on day 4 is due to AE and dose interruption on day 5 is due to dosing error, then the total number of dose interruptions is 2).
- If an interruption occurs for more than one day due to the same reason, but the days are not consecutive, i.e. there is at least one dosing day in between, then each dose interruption will be counted as a different occurrence (example: If the actual dose on days 1, 3 and 5, is 10 mg and actual dose on days 2 and 4 is 0 mg, and dose interruptions on day 2 and 4 are both due to dosing error, the total number of dose interruptions is 2).

A dose interruption is not considered a dose reduction or a dose delay.

The number and percentage of patients with dose interruptions and the corresponding reasons will be summarized.

6.5.3.7. Dose delays

Applicable to avelumab and sunitinib.

Avelumab

Dose delay is the difference between the actual time between two consecutive non-zero doses and the planned time between the same two consecutive non-zero doses.

In Cycle 1,

$$\text{Dose Delay (days)} = \text{day of first dose of avelumab} - 1.$$

After the first dose of Cycle 1

$$\text{Dose Delay (days)} = \text{Date of dose } x \text{ of avelumab} - \text{Date of dose } (x-1) \text{ of avelumab} - 14.$$

Sunitinib

Dose delay is the difference between the actual time between the last non-zero dose of a cycle and the actual first non-zero dose of the next cycle and the planned time between the

same two doses. Dose delay is only calculated for the first dose of sunitinib administered in each cycle.

In Cycle 1,

Dose Delay for Dose 1 (days) = day of first dose of sunitinib – 1.

In Cycle >1

Dose Delay for Dose x (days) = Date of first dose of sunitinib in Cycle x – Date of first dose of sunitinib in Cycle (x-1) – 42

Dose Delays will be grouped into the following categories

- No delay
- 1-3 days delay
- 4-6 days delay
- 7 or more days delay

For example, for avelumab, administered on a 2-week schedule, if one patient receives avelumab on Day 1, then the next avelumab administration date will be on Day 15; however, if the patient receives avelumab at Day 16 or 17, this is considered as 1-3 days delay.

No delay and 1-3 days delay will also be summarized together.

The number and percentage of patients with delayed study drug administration and maximum length of delay, i.e., the worst case of delay if patients have multiple dose delays will be summarized.

6.5.3.8. Infusion rate reductions

Applicable to avelumab.

The number and percentage of patients with at least one infusion rate reduction of $\geq 50\%$ compared to the first infusion rate reported in the eCRF as well as the frequency of patients with 1, 2, 3 or ≥ 4 infusion rate reductions of $\geq 50\%$ or more will be summarized.

6.5.3.9. Infusion interruptions

Applicable to avelumab.

An infusion interruption is defined as an infusion that is stopped and re-started on the same day (i.e., for a visit more than one infusion start time and infusion end time are recorded).

The number and percentage of patients with at least one infusion interruption as well as the frequency of patients with 1, 2, 3, or ≥ 4 infusion interruptions will be summarized.

6.5.4. Concomitant medications and non-drug treatments

The following analyses will be based on the safety analysis set by treatment arm.

Concomitant medications are medications, other than study medications, which started prior to first dose date of study treatment and continued on on-treatment period as well as those started during the on-treatment period. **Prior medications** are medications, other than study medications and pre-medications for study drug, which are started before the first dose of study treatment.

Prior and concomitant medications will be summarized from the 'General Concomitant Medications' eCRF page. Pre-medications for study drug will also be summarized separately from the 'Pre-Medication Treatment' eCRF page.

Summary of prior medications, summary of concomitant medications and summary of pre-medications will include the number and percentage of patients by Anatomical Therapeutic Chemical (ATC) Classification level 2 and preferred term. A patient will be counted only once within a given drug class and within a given drug name, even if he/she received the same medication at different times. If any prior or concomitant medication is classified into multiple ATC classes, the medication will be summarized separately under each of these ATC classes. The summary tables will be sorted on decreasing frequency of drug class and decreasing frequency of drug name in a given drug class. In case of equal frequency regarding drug class (respectively drug name), alphabetical order will be used. In case any specific medication does not have ATC classification level 2 coded term, it will be summarized under 'Unavailable ATC classification' category.

A listing of prior medications and a listing of concomitant medications will be created with the relevant information collected on the 'General Concomitant Medications' eCRF page. A listing of pre-medications will be created with the relevant information collected on the 'Pre-Medication Treatment' eCRF page.

All concurrent procedures, which were undertaken any time during the on-treatment period, will be listed according to the eCRF page 'General Non-drug Treatments'. A listing of concurrent procedures will be created with the relevant information collected on the 'General Non-drug Treatments' eCRF page.

6.5.5. Subsequent anti-cancer therapies

The following analyses will be based on the FAS by treatment arm.

Anti-cancer treatment will be provided in a data listing with data retrieved from 'Follow-up Cancer Therapy', 'Concomitant Radiation Therapy', 'Follow-up Radiation Therapy', 'Concomitant Surgery' and 'Follow-up Surgery' eCRF pages.

Number and percentage of patients with any anti-cancer therapy after discontinuation will be tabulated overall and by type of therapy based on the data collected from the 'Follow-up Cancer Therapy' 'Follow-up Radiation Therapy' and 'Follow-up Surgery' eCRF pages.

6.6. Safety Summaries and Analyses

The Safety Analysis Set will be the primary population for safety evaluations. Summaries of AEs and other safety parameters will be based on the safety analysis set by treatment arm.

6.6.1. Adverse events

Treatment-emergent adverse events (TEAEs) are those events with onset dates occurring during the on-treatment period for the first time, or if the worsening of an event is during the on-treatment period as defined in Section 3.5.1.

All analyses described will be based on TEAEs (started during the on-treatment period) if not otherwise specified. The AE listings will include all AEs (whether treatment-emergent or not). AEs outside the on-treatment period will be flagged in the listings.

- **Related Adverse Events:** adverse events with relationship to study treatment (as recorded on the AE eCRF page, Relationship with study treatment = Related) reported by the investigator and those of unknown relationship (i.e., no answer to the question ‘Relationship with study treatment’). Related AEs are those related to at least one of the study drugs (in Arm A).
- **Serious Adverse Events (SAE):** serious adverse events (as recorded on the AE eCRF page, Serious Adverse Event = Yes).
- **Adverse Events Leading to Dose Reduction:** adverse events leading to dose reduction of study treatment (as recorded on the AE eCRF page, Action taken with study treatment = Dose reduced).
- **Adverse Events Leading to Interruption of Study Treatment:** adverse events leading to interruption of study treatment (as recorded on the AE eCRF page, Action taken with study treatment = Drug interrupted). The eCRF does not allow for a clear separation between interruption of an infusion and delays of administration for a parenteral drug as both are recorded using the same term on the eCRF (“Drug interrupted”). IRRs will be excluded in the analysis of AEs leading to Drug Interruption in case they only led to an interruption of the infusion.
- **Adverse Events Leading to Permanent Treatment Discontinuation:** adverse events leading to permanent discontinuation of study treatment (as recorded on the AE eCRF page, Action taken with study treatment = Drug withdrawn).
- **Adverse Events Leading to Death:** adverse event leading to death (as recorded on the AE eCRF page, Outcome = Fatal, as well as AEs of Grade 5).
- **Immune-related Adverse Events (irAE):** irAEs (as identified according to the methodology outlined in Appendix 1 for a pre-specified search list of MedDRA PTs, documented in the Safety Review Plan and finalized for analysis of the current studies data prior to DB lock)
- **Infusion-related Reactions (IRR):** IRRs (as identified according to the methodology outlined in Appendix 2 for a pre-specified search list of MedDRA PTs, documented in

the Safety Review Plan and finalized for analysis of the current studies data prior to DB lock).

Unless otherwise specified, AEs will be summarized by number and percentage of patients with the AE in the category of interest as described above, by treatment arm, primary SOC and PT in decreasing frequency based on the frequencies observed for Arm A.

Each patient will be counted only once within each SOC or PT. If a patient experiences more than one AE within a SOC or PT for the same summary period, only the AE with the strongest relationship or the worst severity, as appropriate, will be included in the summaries of relationship and severity.

6.6.1.1. All adverse events

Adverse events will be summarized by worst severity (according to NCI-CTCAE version 4.03) per patient, using the latest version of MedDRA preferred term (PT) as event category and MedDRA primary system organ class (SOC) body term as Body System category.

In case a patient has events with missing and non-missing grades, the maximum of the non-missing grades will be displayed. No imputation of missing grades will be performed.

The following tables will be created:

- The overall summary of AEs table will include the frequency (number and percentage) of patients with each of the following by treatment arm:
 - TEAEs
 - TEAEs, Grade ≥ 3
 - Related TEAEs
 - Related TEAEs, Grade ≥ 3
 - TEAEs leading to dose reduction of avelumab
 - TEAEs leading to dose reduction of axitinib
 - TEAEs leading to dose reduction of sunitinib
 - TEAEs leading to interruption of avelumab
 - TEAEs leading to interruption of axitinib
 - TEAEs leading to interruption of sunitinib
 - TEAEs leading to discontinuation of avelumab
 - TEAEs leading to discontinuation of axitinib
 - TEAEs leading to discontinuation of sunitinib
 - TEAEs leading to discontinuation of any study drug
 - TEAEs leading to discontinuation of all study drugs

- Related TEAEs leading to discontinuation of avelumab
- Related TEAEs leading to discontinuation of axitinib
- Related TEAEs leading to discontinuation of sunitinib
- Related TEAEs leading to discontinuation of any study drug
- Related TEAEs leading to discontinuation of all study drugs
- Serious TEAEs
- Related Serious TEAEs
- TEAEs leading to death
- Related TEAEs leading to death
- irAEs
- IRRs
- TEAEs by SOC and PT and worst grade
- Related TEAEs by SOC and PT and worst grade
- TEAEs leading to death by SOC and PT
- Related TEAEs leading to death by SOC and PT
- TEAEs Excluding SAEs, with frequency $\geq 5\%$ in any treatment arm by SOC and PT

6.6.1.2. Adverse events leading to dose reduction

The frequency (number and percentage) of patients with each of the following will be presented for TEAEs leading to dose reduction of each study drug by treatment arm:

- TEAEs leading to dose reduction of avelumab by SOC and PT
- TEAEs leading to dose reduction of axitinib by SOC and PT
- TEAEs leading to dose reduction of sunitinib by SOC and PT

. The listing of all AEs leading to dose reduction will also be provided with the relevant information.

6.6.1.3. Adverse events leading to interruption of study treatment

The eCRF does not allow for a clear separation between interruption of an infusion and delays of administration for a parenteral drug as both are recorded using the same term on the eCRF (“Drug interrupted”). IRRs will be excluded in the analysis of AEs leading to Drug Interruption in case they only led to an interruption of the infusion (ie, did not lead to a dose reduction or a dose delay).

As such, AEs leading to interruption will be defined as AEs identified in the AE eCRF page with an action taken with study treatment of ‘drug interrupted’ excluding

- IRRs that occurred on the day of infusion with $\geq 90\%$ of the planned dose given (ie IRRs that did not lead to a dose reduction) and subsequent administration of study drug had no delay (as defined in Section 6.5.3.7). These IRRs will be considered as IRRs leading to interruption of infusion.
- IRRs occurring on the day after infusion and subsequent dose administration had no delay (as defined in Section 6.5.3.7).

The frequency (number and percentage) of patients with each of the following will be presented for TEAEs leading to interruption of each study drug by treatment arm:

- TEAEs leading to interruption of avelumab by SOC and PT
- TEAEs leading to interruption of axitinib by SOC and PT
- TEAEs leading to interruption of sunitinib by SOC and PT

. The listing of all AEs leading to interruption of study treatment will also be provided with the relevant information.

In addition, the frequency (number and percentage) of patients with each of the following will be presented for TEAEs leading to interruption of each study drug by treatment arm:

- TEAEs leading to both interruption and dose reduction of avelumab by SOC and PT
- TEAEs leading to both interruption and dose reduction of axitinib by SOC and PT
- TEAEs leading to both interruption and dose reduction of sunitinib by SOC and PT

This summary will take into account PTs with both actions as defined in Section 6.6.1, even though the actions may be captured for different PT records (ie, different onset for the PT with action “drug interrupted” and the PT with action “dose reduced”).

6.6.1.4. Adverse events leading to discontinuation of study treatment

The frequency (number and percentage) of patients with each of the following will be presented for TEAEs leading to permanent discontinuation of each study drug and study treatment, by treatment arm:

- TEAEs leading to discontinuation of avelumab by SOC and PT
- Related TEAEs leading to discontinuation of avelumab by SOC and PT
- TEAEs leading to discontinuation of axitinib by SOC and PT
- Related TEAEs leading to discontinuation of axitinib by SOC and PT
- TEAEs leading to discontinuation of sunitinib by SOC and PT
- Related TEAEs leading to discontinuation of sunitinib by SOC and PT
- TEAEs leading to discontinuation of any study drug by SOC and PT

- Related TEAEs leading to discontinuation of any study drug by SOC and PT
- TEAEs leading to discontinuation of all study drugs by SOC and PT
- Related TEAEs leading to discontinuation of all study drugs by SOC and PT.

The listing of all AEs leading to treatment discontinuation will also be provided with the relevant information.

6.6.2. Deaths

The frequency (number and percentage) of patients in the safety analysis set who died and who died within 30 days after last dose of study treatment as well as the reason for death, will be tabulated based on information from the 'Notice of Death' and 'Survival Follow-Up' eCRFs, by treatment arm.

- All deaths
- Deaths within 30 days after last dose of study treatment
- Reason for Death
 - Disease progression
 - Study treatment toxicity
 - AE not related to study treatment
 - Unknown
 - Other.

In addition, date and cause of death will be provided in individual patient data listing together with selected dosing information (study treatment received, date of first / last administration, dose) and will include the following information:

- AEs with fatal outcome (list preferred terms of AEs with outcome=Fatal, as well as AEs of Grade 5),
- Flag for death within 30 days of last dose of study treatment.

6.6.3. Serious adverse events

The frequency (number and percentage) of patients with each of the following will be presented for treatment-emergent SAEs by treatment arm:

- SAEs by SOC and PT
- Related SAEs by SOC and PT

The listings of all SAEs will also be provided with the relevant information with a flag for SAEs with onset outside of the on-treatment period.

6.6.4. Other significant adverse events

The frequency (number and percentage) of patients with each of the following will be presented for irAEs, by treatment arm:

- irAEs leading to death, by Cluster and PT
- irAEs, by Cluster and PT
- irAEs, Grade ≥ 3 , by Cluster and PT
- irAEs leading to discontinuation of avelumab, by Cluster and PT
- irAEs leading to discontinuation of axitinib, by Cluster and PT
- irAEs leading to discontinuation of sunitinib, by Cluster and PT
- irAEs leading to discontinuation of any study drug, by Cluster and PT
- irAEs leading to discontinuation of all study drugs, by Cluster and PT
- Serious irAEs, by Cluster and PT

The listing of all irAEs will also be provided with the relevant information with a flag for irAEs with onset outside of the on-treatment period.

The frequency (number and percentage) of patients with each of the following will be presented for IRRs, by treatment arm:

- IRRs leading to death, by PT
- IRRs, by PT
- IRRs, Grade ≥ 3 , by PT
- IRRs leading to discontinuation of avelumab, by PT
- Serious IRRs, by PT
- Time related to first onset of an IRR (infusion 1, infusion 2, infusion 3, infusion 4 or later)

The listing of all IRRs will also be provided with the relevant information with a flag for IRRs with onset outside of the on-treatment period.

In addition, the following analyses will be presented for Tier-1 (irAEs and IRRs as defined in Appendices 1 and 2) and Tier-2 events separately. P-values and CIs for risk difference will be calculated based on the unconditional exact method by Santner and Snell (1980). No additional analyses will be presented for Tier-3 AEs.

- Frequency (number and percentage) of patients with each of the following by treatment arm and PT or Clustered Term:

- Tier-2 AEs
- Tier-2 AEs Grade ≥ 3
- Point estimate for risk difference and 95% CI for risk difference (experimental arm vs comparator arm) for each of the following by PT or Clustered Term:
 - irAEs
 - irAEs Grade ≥ 3
 - Tier-2 AEs
 - Tier-2 AEs Grade ≥ 3
- 2-sided p-value associated with risk difference (experimental arm vs comparator arm) for each of the following by PT or Clustered Term:
 - irAEs
 - irAEs Grade ≥ 3
- The p-values and CIs reported are not adjusted for multiplicity and should be used for screening purposes only. The 95% CIs are provided to help gauge the precision of the estimates for the risk difference and should be used for estimation purposes only.

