The sample size for this study is determined based on the following:

1. the median PFS for patients receiving sunitinib is 11 months (Sutent Summary of Product Characteristics) and the median PFS for patients receiving avelumab in combination with axitinib is 16.9 months for PD-L1 positive patients and 15.7 months for patients unselected for PD-L1 expression; this, corresponds to a hazard ratio (HR) of 0.65 and 0.7, respectively under the exponential model assumption;
2. the median OS for patients receiving sunitinib is 26.4 months (Sutent Summary of Product Characteristics) and the median OS for patients receiving avelumab in combination with axitinib is 37.7 months for PDL1 positive patients and 35.2 months for patients unselected for PD-L1 expression; this corresponds to a HR of 0.7 and 0.75, respectively under the exponential model assumption;

3. PFS drop-out rate of approximately 15% and OS drop-out rate of approximately 5%;
4. 70% of the randomized patients are PD-L1 positive;
5. non-uniform patient accrual accomplished over a 21 month period.

The sample size of approximately 830 patients will also allow an assessment of PFS and OS in patients unselected for PD-L1 expression.

If H_{01} is rejected then PFS in patients unselected for PD-L1 expression can be tested and 490 PFS events by BICR assessment will be required to have at least 90% power to detect a HR of 0.70 using a 1-sided log rank test at a significance level of 0.004, and a 2-look group sequential design with Lan-DeMets (O'Brien-Fleming) α -spending function to determine the efficacy boundary.

If either H_{02} or H_{03} are rejected, then OS in patients unselected for PD-L1 expression can be tested at the sum of the significance levels associated with the significant H_{02} and H_{03} tests (see Figure 1). With 534 OS events, the power is 91% (if both H_{02} and H_{03} are rejected), 90% (if H_{02} is rejected and H_{03} is not rejected) or 74% (if H_{02} is not rejected and H_{03} is rejected) to detect a HR of 0.75 using a 1-sided log rank test at a significance level of 0.025, 0.021 or 0.004, respectively, and a 4-look group sequential design with Lan-DeMets (O'Brien-Fleming) α -spending function to determine the efficacy boundary.

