5.2.7. Definition of on-treatment period

Safety endpoints will be summarized based on the on-treatment period unless otherwise specified.

On-treatment period is defined as the time from the first dose of study treatment through minimum (30 days + last dose of study treatment, start day of new anti-cancer drug therapy – 1 day).

Safety data collected outside the on-treatment period as described above will be listed and flagged in listings but will not be summarized.

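### The planned between-arm adverse-event comparisons use crude percentages only; adding time-aware tables would be a cheap improvement, because Arm A is probably observed longer if the efficacy hypothesis holds

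*SAP*

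**What the plan says.** - **Unit of count.** SAP 6.6.1: "Unless otherwise specified, AEs will be summarized by number and percentage of patients with the AE" in the category concerned. Person-time does not enter.
- **Comparison.** SAP 6.6.4 gives risk differences with 95% CIs for irAEs and Tier-2 events, each for all grades and Grade ≥3: "P-values and CIs for risk difference will be calculated based on the unconditional exact method by Santner and Snell (1980". The "2-sided p-value associated with risk difference (experimental arm vs comparator arm") is listed for irAEs and Grade ≥3 irAEs only.
- **Status.** SAP 6.6.4: "The p-values and CIs reported are not adjusted for multiplicity and should be used for screening purposes only". It adds that the CIs serve estimation. SAP 3.5.1 calls safety analyses exploratory.
- **Window, treatment-emergent events.** SAP 5.2.7: "On-treatment period is defined as the time from the first dose of study treatment through minimum (30 days + last dose of study treatment", or the day before a new anti-cancer drug if that is sooner. Under SAP 3.4.1, Arm A's last dose is the later of its two drugs.
- **Window, irAEs.** SAP Appendix 1, Table 18, step 2, runs to 90 days after last dose, whether or not a new anti-cancer drug has been started.
- **Treatment length.** Protocol 3.1.1 treats both arms until progression is confirmed by central review, with earlier stopping for toxicity or refusal. Protocol 5.4.4 permits treatment past progression.
- **Design assumption.** SAP 5.1.1 takes median PFS as 11 months on sunitinib. For the combination it takes 16.9 months in PD-L1 positive patients and "15.7 months for patients unselected for PD-L1 expression".

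**The concern.** A crude percentage depends on the rate at which events occur and on how long patients are watched. Here the watching time is tied to time on treatment, and time on treatment is tied largely to progression. If the combination delays progression as the design assumes, Arm A accrues more window time. Its percentages then rise for any event that keeps accruing, even when monthly toxicity is equal. The gap also widens with follow-up, so the same table could read differently at the PFS analysis and at the final OS analysis with no change in toxicity.

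SAP 6.5.3 summarizes exposure by arm but never links it to adverse-event incidence, and SAP 6.6 contains no rate per unit of time and no time-to-first-event comparison. Two time-aware analyses described in Protocol 9.5 are also missing from the SAP. The protocol plans adverse-event summaries by cycle, and SAP 6.6.1 to 6.6.4 list none. The protocol plans Kaplan-Meier curves for time to discontinuation due to toxicity, and SAP 6.6.5 gives only means, medians and quartiles.

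**Working it through.** **1. The plan's own figure.** Under exponential PFS, 11/16.9 = 0.651 and 11/15.7 = 0.701, which match the stated hazard ratios of 0.65 and 0.70. Schoenfeld's formula gives 4(2.652 + 1.282)²/(ln 0.65)² ≈ 334 events for 90% power at one-sided 0.004, against 336 stated. The assumed PFS gap is therefore reproduced.

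**2. Inputs to the model.**
- From the documents: PFS medians 11 and 15.7 months; 30-day tail (30/30.4375 = 0.986 months); 21-month accrual; 830/2 = 415 per arm; cut-offs at months 32, 46 and 61 (SAP Tables 7 and 8, alternative hypotheses).
- Assumed, because the documents give no figure: equal constant monthly first-event hazard L in both arms; exponential time on treatment T with median equal to the arm's assumed PFS median; uniform accrual (the plan says non-uniform); an equal extra stopping hazard of 0 to 4% per month for reasons other than progression; Arm B percentages of 20% and 30%.

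**3. Formula.** With W = min(T + 0.986, cut-off − entry), the crude percentage is 1 − E[exp(−L·W)]. L is solved so that Arm B equals the chosen percentage. For 30%, with no extra stopping, L = 0.0316 at month 32 and 0.0253 at month 61.

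**4. Results for the 30-day window.**

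| Cut-off (month) | Mean window B / A, no extra stopping | Arm A when B = 20%, no extra stopping | Arm A when B = 30%, no extra stopping | Arm A when B = 30%, 4%/month extra stopping |
|---|---|---|---|---|
| 32 | 12.2 / 14.1 | 22.9% | 34.0% | 33.0% |
| 46 | 14.9 / 18.5 | 24.2% | 35.7% | 33.8% |
| 61 | 16.1 / 21.0 | 25.1% | 36.8% | 34.0% |

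For the 30% event with no extra stopping, a normal approximation puts the chance that a 95% CI excludes zero at about 24% (month 32) and 54% (month 61). With 4% per month extra stopping it is about 16% and 23%.

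**5. irAE window.** With the 90-day tail, full follow-up and no extra stopping, 10% in Arm B becomes 13.1% in Arm A, and 20% becomes 25.4%.

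**6. Early-onset events.** If the hazard acts only in the first 3 months, 10%, 20% and 30% in Arm B become 10.1%, 20.2% and 30.3% in Arm A. The distortion is at most about 0.3 points.

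**7. How the alternatives behave.**
- *Exposure-adjusted rate* (first events divided by patient-months at risk). Under a constant equal hazard the expected A/B ratio is 1.00. In 4,000 simulated trials (20% event, full follow-up) the crude comparison rejected in 52.9% and the rate ratio in 5.2%. For the early-onset events of step 6, however, the ratio falls to about 0.87 at month 32 and 0.78 at month 61, which wrongly favours Arm A.
- *Cumulative incidence at a fixed time t*, with window end as a competing event. Let h = ln 2/median and c = 0.986. Then F(t) = 1 − e^(−Lc) + [L·e^(hc)/(L+h)]·[e^(−(L+h)c) − e^(−(L+h)t)]. With L = 0.0253 and t = 12, F = 19.8% in Arm B (h = 0.0630) and 21.5% in Arm A (h = 0.0441). The gap is about 1.6 points before rounding, against 6.8 for the crude percentage at month 61. This measure does not move with the cut-off, but it keeps the effect of treatment length up to t.

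**The case against.** The strongest reply is that nothing is decided on these numbers. They are labelled screening or estimation only, p-values are confined to irAEs, and equal toxicity is not a realistic null for irAEs between a PD-L1 antibody combination and sunitinib. Crude percentages also answer a fair question: what happens over the course of treatment as given. All of this stands. It makes the matter one of interpretation, not of error control. It does not make the estimate free of exposure, and a screen that responds to time on treatment is a weaker screen.

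Three stronger readings are tempting and are not supported.

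- A reader might infer that the plan itself expects Arm A to be treated longer. It states no treatment duration. Longer treatment is inferred from the PFS assumption plus treatment to progression, and stopping for toxicity or treating past progression could narrow or widen the gap.
- A reader might infer that Arm A must show more toxicity for every event. That needs a hazard that persists, and step 6 shows almost no effect for early events.
- A reader might conclude that exposure-adjusted rates should replace the crude differences. Step 7 shows that they can err in the opposite direction.

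**Conclusion.** The gap is real and modest. SAP 6.6.4 offers only crude risk differences for irAEs and Tier-2 events, with windows that lengthen with treatment. Given the assumed PFS medians, equal constant hazards and 0–4% per month stopping for other reasons, a 30% event in Arm B would show as about 33–34% in Arm A at month 32 and 34–37% at month 61. The excess is near zero for events confined to the first 3 months. The direction depends on the efficacy hypothesis being true and on stopping for other reasons not offsetting it. The conclusion is a cheap improvement to safety reporting. It does not touch the primary or key secondary tests.

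**What to change.** In SAP 6.6.4, keep the crude risk differences and add the following for irAEs and Tier-2 events, all grades and Grade ≥3:

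1. Cumulative incidence of first event by arm, with estimates at fixed times (for example 6 and 12 months). Treat death, and the end of the adverse-event window for any reason other than the data cut-off, as competing events.
2. Exposure-adjusted first-event rates by arm, with a rate ratio or difference and 95% CI. Use the 90-day window of Appendix 1 for irAEs and the on-treatment period of SAP 5.2.7 for other events.
3. A sentence saying that the crude, rate and cumulative-incidence results are read together and that no between-arm statement rests on rates alone.

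Also carry over from Protocol 9.5 the by-cycle adverse-event summaries, and in SAP 6.6.5 the Kaplan-Meier analysis of time to discontinuation due to toxicity with its censoring rule. If either is dropped deliberately, say so.

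Onset dates, dosing dates and deaths are already collected, so the cost is SAP wording and a few extra tables. The limitations are the roughly constant hazard behind the rates, and the treatment-length effect that remains in cumulative incidence up to the chosen time.
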